## **PROTOCOL FOR HUM00108213: Brain stimulation in aphasia**

### **Research Design**

#### 5-1.1 Objective

This project will focus on treating aphasia with tDCS in conjunction with language therapy.

#### 5-1.2 Specific Aim/Hypothesis

We are interested in determining if and how tDCS can be used as a tool to improve language ability in aphasic patients when used in conjunction with language therapy. We would like to assess the patient-specific parameters under which tDCS is effective: specifically, whether factors like lesion size and location, aphasia severity and type, and time post-stroke influence the efficacy of tDCS with language therapy.

#### 5-1.3 Background Information

There has been research to support the idea that tDCS can have beneficial effects on aphasia when applied to the left hemisphere, typically around Broca's area (Aguiar, Paolazzi, & Miceli, 2015). These effects have been observed in studies with tDCS administered for ten minutes (Baker et al., 2010) to thirty minutes (Lee et al., 2013), over one session (Rosso et al., 2014) to ten sessions (Galletta & Vogel-Eyny, 2015; de Aguiar et al., 2015) with non-fluent (Campana, Caltagirone, & Marangolo, 2015; Shah-Basek et al., 2015) and fluent aphasics (Jung et al., 2011; Fridriksson et al., 2011). Although tDCS is often beneficial, there is a need for a targeted approach to assess the stimulation-specific and patient-specific parameters under which tDCS is a successful tool. Additionally, studies using tDCS in aphasic patients have not employed traditional language therapy in their sessions; instead, they often target one outcome like word retrieval (Baker et al., 2010; Floel et al., 2011; Fiori et al., 2011). Limited work has been done to determine whether stimulation can improve outcomes with traditional therapy.

#### 5-1.5 Methodology

Subjects will be recruited from the University of Michigan Aphasia Program. In this clinical program, clients undergo intensive language therapy over four weeks which includes a combination of individual therapy (about 14 hours a week), group therapy (about 6 hours a week), and computer-based therapy (about 5 hours a week). This project will consist of tDCS sessions administered during the course of this clinical care. Subjects will receive up to 30 sessions of active tDCS over the left hemisphere while undergoing individual behavioral therapy. The standard numeric analogue scale used for pain in UMHS with the addition of faces on a scale of 1 to 10 will be placed in front of the client to allow them to communicate any discomfort they may feel and if they would like to stop the study.

#### 5-1.6 Statistical Design

We will compare the baseline performance of subjects to their performance after tDCS in conjunction with language therapy, including specific measures of word fluency and naming. We have data collected from a group of 300 subjects who received the same type of therapy without tDCS which we can use as a “control group” to compare the effect of therapy alone to the effect of therapy with tDCS. We will also assess subject parameters as they relate to their performance, including age, time post-stroke, type and severity of aphasia, location and size of lesion, and other relevant variables. If possible, we will also have follow-up meetings with the subjects either 4 weeks post-therapy or 8 weeks post-therapy to see how long improvement is maintained.

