### **Participants**

Recruitment: Clients who are participating in the University of Michigan Aphasia Program and meet study criteria will be invited to join this study. Clients who are identified by the [name] as a potential subject, will first be asked if they would like to hear about the study from a member of the research team. If the patient consents, then the member of the research team will meet with the patient and a family member if present to discuss the study. Only subjects with aphasia will participate in this study.

Inclusion criteria: Chronic receptive or expressive aphasia with or without apraxia.

Exclusion criteria: Any implanted devices or surgical instruments, history of severe mental illness or epilepsy, no active history of seizures (within three months). As the risks to pregnancy, are unknown, no pregnancy or plan to become pregnant during the study period will also be an exclusion criteria.

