### **tDCS**

Parameters: All subjects will receive up to 30 sessions of active tDCS. Depending on the availability of the subject, the session number may vary from 15 to 30 sessions. Each session will begin with up to 20 minutes of active tDCS at 2mA in conjunction with the individual behavioral therapy. The anode electrode will be placed over the left hemisphere and the reference electrode will be placed on the contralateral frontopolar cortex. The specific montage will be determined based on individual patient characteristics.

Risks: tDCS is generally considered safe with no more than minimum risk. In a meta-analysis of over 200 tDCS studies conducted from 1998 to 2010, 56% of studies mentioned adverse events (Brunoni et al., 2011). The available evidence suggests that it is safe. However, it is investigational in nature, which means that we are doing these studies to learn more about tDCS. The most common side effects associated with tDCS based on the available scientific data are:

Sensations under the electrode: These sensations usually stop shortly after tDCS begins but can sometimes continue throughout and for a brief period after tDCS.

- Mild tingling • Light itching • Slight burning sensation • Discomfort

Effects reported that occur ONLY during tDCS:

- Visual sensation during switching on and off the stimulation

Other effects that can occur both during and after tDCS include:

- Fatigue,
- Skin redness
- Headache
- Changes in concentration, memory, or other cognitive abilities. This is partially what we will be testing.

Additionally the following rare side effects have been described in previous studies that used tDCS:

- Nausea
- Nervousness
- It is also possible that the electric current can cause a burn on your skin. This is unlikely because we are using a smaller dose than what is known to cause burns and because we use saline or gel to reduce electrical resistance that leads to burns.
- A shock-like sensation at the initiation of tDCS was reported in one participant.
- Changes in the activity of the prefrontal region (front of the head) have the potential to induce sudden changes in your mood. Hypomania has been reported in a few patients receiving tDCS for bipolar disorder and depression but never in normal controls.

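### The only treatment-effect comparison the plan commits to is before-after, which cannot separate tDCS from the concurrent therapy; the 300 therapy-only subjects who could separate them are left optional and unspecified

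*Combined protocol and SAP*

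**What the plan says.** Section 5-1.6 (Statistical Design) opens with the commitment: "We will compare the baseline performance of subjects to their performance after tDCS in conjunction with language therapy". Word fluency and naming are the measures it names. The external data come next, in permissive wording: "We have data collected from a group of 300 subjects who received the same type of therapy without tDCS which we can use". Their intended role is that of controls, setting therapy alone against therapy with tDCS.

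Two further analyses follow. One is "We will also assess subject parameters as they relate to their performance, including age, time post-stroke, type and severity of aphasia", together with lesion location and size. The other is follow-up of the same subjects at 4 or 8 weeks after therapy, if possible. Neither contrasts tDCS with no tDCS.

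On treatment, the tDCS section says "All subjects will receive up to 30 sessions of active tDCS". Section 5-1.5 places those sessions inside a programme in which "clients undergo intensive language therapy over four weeks which includes a combination of individual therapy (about 14 hours a week"), plus about 6 hours of group and 5 hours of computer-based therapy a week.

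The aim in section 5-1.2 is "determining if and how tDCS can be used as a tool to improve language ability in aphasic patients" when given with language therapy. Section 5-1.3 states the gap as "Limited work has been done to determine whether stimulation can improve outcomes with traditional therapy".

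**The concern.** The aim and the stated gap concern added benefit: what stimulation contributes beyond therapy. The committed comparison describes only the combined treatment. If its result were read as a tDCS effect, a gain produced entirely by therapy would count as evidence for stimulation.

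The comparison that could remove the shared therapy gain is named but not fixed. The plan designates no primary analysis and ties no conclusion to the 300 subjects. It does not say whether they have the same word fluency and naming measures. Nor does it say whether they would pass this study's exclusions, such as "Any implanted devices or surgical instruments, history of severe mental illness or epilepsy". Age, severity, time post-stroke and lesion variables are to be related to performance, but are not named as adjusters for the group comparison. The choice of comparison, controls and covariates therefore stays open until results are known.

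**Working it through.** **No plan figure to reproduce.** The documents give no treated sample size, effect size, SD, alpha or power. The 300 is a count of existing data. The structural point comes from the text; the arithmetic below only illustrates its size.

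**Step 1: what the before-after change contains.** Concurrent therapy is 14 + 6 + 5 = 25 hours a week, or about 100 hours over four weeks. For each subject:

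change = therapy gain + retest and time effects + tDCS effect

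All subjects have all three components, so infinitely many splits between therapy and tDCS give the same expected change. No before-after analysis of this group can tell them apart.

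**Step 2: before-after test when tDCS adds nothing.** Assumed: two-sided 5% paired t-test; n = 20 or 30; therapy-only gain g in SDs of change. The statistic is noncentral t with n − 1 degrees of freedom and noncentrality g√n. For example, at g = 0.5 and n = 20 the noncentrality is 0.5 × √20 = 2.236, against a critical value of 2.093.

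| g | n = 20 | n = 30 |
|---|---|---|
| 0.3 | 25% | 36% |
| 0.5 | 56% | 75% |
| 0.8 | 92% | 99% |

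These are probabilities of a significant result with zero tDCS effect. The test is correctly detecting the therapy gain; the error arises only if the gain is attributed to tDCS.

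**Step 3: comparison with the 300 when tDCS adds nothing.** Assumed: two-sided 5% two-sample t-test on change, equal SDs, all 300 usable. Let b be the difference in mean change due to selection, in SDs. The noncentrality is b / √(1/n + 1/300), with n + 298 degrees of freedom. At b = 0.3 and n = 20 this is 0.3 / √(1/20 + 1/300) = 1.299.

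| b | n = 20 | n = 30 |
|---|---|---|
| 0 | 5% | 5% |
| 0.1 | 7% | 8% |
| 0.2 | 14% | 18% |
| 0.3 | 25% | 35% |

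The shared therapy gain cancels, so the error rate no longer depends on g. It now depends on how comparable the groups are, which is why restriction and adjustment belong in the plan.

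**Step 4: precision cost.** With m controls and equal SDs, the ratio of the between-group to the before-after standard error is √(1 + n/m).

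| m | n = 20 | n = 30 |
|---|---|---|
| 300 | 1.033 | 1.049 |
| 150 | 1.065 | 1.095 |
| 100 | 1.095 | 1.140 |

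Any precision gained from baseline adjustment is ignored.

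**The case against.** The strongest reply is that the criticism leans on one verb. Section 5-1.6 names the comparator, its size, its therapy and its purpose, so a fair reader may take the permissive wording as informal language for a planned analysis. That reading is plausible. It does not rescue the plan, because what it yields is an external comparison with no restriction, adjustment or stated common measures, which is open to the selection bias in step 3. Nothing elsewhere in the documents supplies what is missing.

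Second, the protocol never says the before-after change will be read as a tDCS effect. That is correct, and the step 2 percentages are conditional on such a reading.

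Third, every numerical input is assumed, including the fall in imbalance from 0.3 to 0.1 SD. This also stands: the tables illustrate a mechanism and do not measure this trial.

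Fourth, this is an open-label project with no confirmatory claim, and its aim also covers which patients benefit. That argues for modest expectations. But asking in whom tDCS works also requires a contrast with no tDCS, so the gap remains.

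Lastly, therapy records may lack lesion data or tDCS-specific exclusions. The fix has to allow for that.

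**Conclusion.** The concern holds and needs correcting before analysis. As worded, the plan could be followed exactly without ever estimating the effect of adding tDCS to therapy. That conclusion comes from the text and rests on no assumed number.

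The size is illustrative. Under the assumptions of steps 2 and 3, with no tDCS effect, the before-after test is significant in 25% to 99% of trials across the gains and sample sizes shown. An unadjusted comparison with the 300 is significant in 25% to 35% if selection shifts mean change by 0.3 SD. The comparator is not absent; it is uncommitted and unspecified. Even when specified, the comparison would be non-randomised and without sham.

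**What to change.** In section 5-1.6:

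1. Make the primary analysis the difference between tDCS and therapy-only subjects in change from baseline to the end of therapy on the word fluency and naming measures, with a 95% confidence interval. State that the therapy-only data will be used.
2. Restrict the 300 to those who meet the criteria under Participants, as far as records allow, and who have the same measures. Report how many remain.
3. Adjust for baseline score and the variables the section already lists: age, time post-stroke, aphasia type and severity, and lesion location and size where available.
4. Label the before-after change as descriptive of the combined treatment, and draw no conclusion about tDCS efficacy from it alone.
5. State that the group comparison is non-randomised and without sham, so selection, calendar-time and placebo effects may remain.

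If the records cannot support items 2 and 3, limit conclusions to the combined treatment.

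The cost is protocol wording and a check of the 300 records, with no new patients. Some controls may be lost. At an assumed 20 to 30 treated subjects, the standard error is about 3–5% larger than for the before-after change with all 300 usable, 6–10% with 150 and 10–14% with 100.

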Subjects with a history of bipolar disorder will be excluded from the study. At this time, tDCS has never been reported to cause a seizure in any patient population. Seizures are, however, theoretically possible and a seizure plan is in place for such an unlikely event. Importantly, the majority of the above side effects have been also reported in association with sham (fake) tDCS, even with similar rates. The table below comes from a recent review of tDCS safety and shows the percentage of studies reporting these common sensations (Brunoni et al., 2011) These data suggest that other factors may cause these sensations, such as your expectations or the pressure of head straps or caps.

**Table 3.** Frequency of adverse effects in 117 (active group) and 82 (sham group) experiments. We considered the presence of adverse effect if the study reported its occurrence in at least one patient

Sensation	Active group	Sham group
Itching	46 (39.3%)	27 (32.9%)
Tingling	26 (22.2%)	15 (18.3%)
Headache	17 (14.8%)	13 (16.2%)
Burning	10 (8.7%)	8 (10%)
Discomfort	12 (10.4%)	11 (13.4%)
Total	117 studies	82 studies

Due to the investigational study, there may be risks, side effects that are not yet

nature of this discomforts or known.

We will follow current safety guidelines for tDCS and will use a current strength of up to 2mA and a duration of up to 20 minutes. Few, if any, side effects are reported with these parameters (Nitsche & Paulus, 2011). We will also monitor subjects for discomfort during and after each session. During the session, we will verbally ask the subject if they are experiencing discomfort. The Speech-Language Pathologists will be in the room while the stimulation is being applied and will consequently be available to assist the patients in communicating any side effects they may be experiencing. After the sessions, subjects will complete the following post-tDCS questionnaire:

tDCS Adverse Effects Questionnaire – Session \_\_\_\_\_

---

Do you experience any of the following symptoms or side-effects?	Enter a value (1–4) in the space below (1, absent; 2, mild; 3, moderate; 4, severe)	If present: Is this related to tDCS? (1, none; 2, remote; 3, possible; 4, probable; 5, definite)	Notes
Headache			
Neck pain			
Scalp pain			
Tingling			
Itching			
Burning sensation			
Skin redness			
Sleepiness			
Trouble concentrating			
Acute mood change			
Others (specify)			

---

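### The 300 therapy-only controls are not restricted to people who would meet this protocol's eligibility criteria, and no matching or adjustment is planned, so eligibility (chronicity above all) may be confounded with tDCS

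*Combined protocol and SAP*

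**What the plan says.** Section 5-1.6 (Statistical Design) plans two comparisons. The first sets each subject's performance after treatment against that subject's own baseline. The second uses an existing dataset: "We have data collected from a group of 300 subjects who received the same type of therapy without tDCS". Its purpose is "to compare the effect of therapy alone to the effect of therapy with tDCS". The section gives no eligibility rule, selection rule or calendar period for the 300, and does not name the programme that treated them.

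The eligibility criteria appear elsewhere and are attached to the people being recruited. Under Participants: "Clients who are participating in the University of Michigan Aphasia Program and meet study criteria will be invited to join this study". Inclusion requires "Chronic receptive or expressive aphasia with or without apraxia". The exclusion list begins "Any implanted devices or surgical instruments, history of severe mental illness or epilepsy, no active history of seizures (within three months" and goes on to pregnancy. The tDCS section adds a further exclusion: "Subjects with a history of bipolar disorder will be excluded from the study".

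Section 5-1.6 also lists patient characteristics (among them age, aphasia type and severity, lesion site and size, and time since stroke) to be studied in relation to performance. It does not name them as matching or adjustment variables for the comparison with the 300.

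**The concern.** Every enrolled subject receives active stimulation, and there is no sham or concurrent untreated arm. The before-after comparison cannot separate tDCS from the intensive therapy given alongside it, which section 5-1.5 puts at about 14 + 6 + 5 = 25 hours a week. The comparison with the 300 is the only planned analysis that could do so, which makes the definition of that group important.

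As written, one side of the comparison is filtered and the other is not said to be. Chronic aphasia is required of tDCS subjects but not stated for the 300. Section 5-1.2 itself asks whether time since stroke influences efficacy, so the plan treats it as potentially important. Several exclusions are tied to stimulation: the tDCS section discusses hypomania and the theoretical possibility of seizure, and Participants cites unknown risk in pregnancy. That the implant, epilepsy and mental-illness exclusions share this rationale is a reasonable inference. People who never received tDCS had no stated reason to be screened for any of these.

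If some of the 300 would fail the criteria and their language gains differ, part of the observed difference in naming or word fluency would reflect who was allowed in. It could go either way. Controls in an earlier recovery phase could raise the control gain and mask a tDCS effect; controls with relevant comorbidity could lower it and mimic one. Nothing in the plan stops one person from contributing a therapy-only course to the 300 and later enrolling for tDCS, although nothing shows that this has happened.

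**Working it through.** **Nothing to reproduce.** The documents give no tDCS sample size, SD, effect size, alpha or power. The figure 300 is a count of existing records. What follows shows scale only, on assumed inputs.

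**Inputs**
- Controls: 300 (section 5-1.6).
- p, the share of the 300 who would fail the criteria: assumed 5% to 50%.
- d, the absolute difference in mean gain between ineligible and eligible controls, in SD units: assumed 0.2 to 0.8.
- n, the number of tDCS subjects: assumed 20, 50 or 100.
- Two-sided alpha: assumed 5%.

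**Bias.** Using all 300 instead of the eligible subset shifts the control mean by p × d in absolute size. If ineligible controls gain more than eligible ones, the tDCS effect is understated; if they gain less, it is overstated.

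**Standard error of the difference with all controls.** SE = √(1/n + 1/300), in SD units:
- n = 20: √(0.0500 + 0.0033) = 0.231
- n = 50: √(0.0200 + 0.0033) = 0.153
- n = 100: √(0.0100 + 0.0033) = 0.115

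This is the right yardstick for the bias. The standard error of the control mean alone, 1/√300 = 0.058, would make the bias look more important than it is for the comparison.

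**False-positive rate** when tDCS has no effect, by the normal approximation: Φ(b/SE − 1.96) + Φ(−b/SE − 1.96), where b is the bias.

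| p | d | b = p × d | n = 20: b/SE | n = 20: rate | n = 50: rate | n = 100: rate |
|---|---|---|---|---|---|---|
| 5% | 0.2 | 0.01 | 0.04 | 5.0% | 5.1% | 5.1% |
| 10% | 0.5 | 0.05 | 0.22 | 5.5% | 6.2% | 7.2% |
| 20% | 0.5 | 0.10 | 0.43 | 7.2% | 10.0% | 13.9% |
| 30% | 0.5 | 0.15 | 0.65 | 10.0% | 16.6% | 25.5% |
| 50% | 0.8 | 0.40 | 1.73 | 41% | 74% | 93% |

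The result runs from negligible to serious, and nothing in the documents places the trial within that range.

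**Precision cost of restricting the controls.** SE = √(1/n + 1/m), where m is the number of controls kept. If half are dropped, m = 150:
- n = 20: from 0.231 to √(0.0500 + 0.0067) = 0.238, a ratio of 1.03
- n = 50: from 0.153 to 0.163, a ratio of 1.07
- n = 100: from 0.115 to 0.129, a ratio of 1.12

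The loss is small because the tDCS group limits precision. It grows if that group is large.

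**The case against.** The strongest reply is that the protocol is silent, which is not the same as saying that the criteria are withheld from the 300. Section 5-1.6 says only that the data can be used as a control group, which leaves room for later restriction. The therapy is described as of the same type, which suggests overlapping clienteles. A reader might infer that the two groups come from different populations, or that the 300 do include non-chronic clients, people with epilepsy or implants, or people who later had tDCS. The documents support none of these statements. What stands is narrower: the controls are not shown to be drawn from the same eligible population.

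It is also fair to say that the documents do not link implants, pregnancy or psychiatric history to language gain, that opposing influences may partly cancel, and that every input to the bias calculation is assumed. All of this stands, and it rules out any claim about actual size or direction. Chronicity is the exception in relevance, because the protocol itself singles out time since stroke. That variable is already among those to be assessed, but assessing it in relation to performance does not commit the plan to adjusting the comparison for it.

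Finally, restricting the controls addresses only one weakness of a non-randomised external control group. This is correct, and the fix should say so.

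**Conclusion.** The concern holds in limited form. The control set is undefined with respect to eligibility, and the comparison has no stated matching or adjustment, so using all 300 as described may confound eligibility, notably chronicity, with tDCS. The illustrative bias of 0.01 to 0.40 SD rests wholly on assumed shares, gain differences and tDCS sample sizes, and no direction can be given. A reader should not conclude that the comparison is in fact biased or that the populations differ: the documents establish only that comparability is neither shown nor secured.

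The before-after comparison is untouched by this point. The change is worth making because it is cheap, it replaces an open choice with a rule fixed before the groups are compared, and it bears on the only analysis that could attribute improvement to tDCS.

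**What to change.** First reconcile the exclusion list under Participants. Its seizure and pregnancy items are worded as absences, so that, read literally as exclusions, they would remove people without seizures or pregnancy. The list also needs to be aligned with the bipolar exclusion in the tDCS section. The investigators must settle what was intended before the criteria can be applied to anyone's records.

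Then amend section 5-1.6 along these lines:

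*The control set comprises those of the 300 therapy-only subjects whose existing records at entry show that they meet the inclusion criterion and none of the exclusions of this protocol as reconciled. Criteria that the records cannot show will be listed and reported as a limitation. Each person contributes one course of therapy, and nobody enrolled for tDCS is counted as a control. The comparison will be adjusted for baseline score and, where available, for age, time since stroke, aphasia type and severity, and lesion location and size. The number of controls retained, and the number removed under each criterion, will be reported. The comparison with all 300 will be shown as a sensitivity analysis only.*

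The cost is a review of existing records, one paragraph of protocol text and the modest precision loss shown above. Some controls may lack lesion data or psychiatric history, so the plan should say how missing items are handled. Differences due to invitation, consent, availability for sessions and calendar time will remain and should be stated as limitations.

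### The contrast of therapy with tDCS against therapy alone appears to confound group with period, and the plan has no check for drift

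*Combined protocol and SAP*

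**What the plan says.** Section 5-1.6 (Statistical Design) describes two comparisons. The first is within subjects: "We will compare the baseline performance of subjects to their performance after tDCS in conjunction with language therapy". The second is between groups and relies on existing records: "We have data collected from a group of 300 subjects who received the same type of therapy without tDCS". Its stated purpose is "to compare the effect of therapy alone to the effect of therapy with tDCS". The plan itself puts the term control group in quotation marks.

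The tDCS group is prospective. Section 5-1.5 says "Subjects will be recruited from the University of Michigan Aphasia Program", and the tDCS section says "All subjects will receive up to 30 sessions of active tDCS". No sham, randomised or concurrent therapy-only group is described.

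On covariates, 5-1.6 says "We will also assess subject parameters as they relate to their performance, including age, time post-stroke, type and severity of aphasia", and goes on to lesion location and size and other relevant variables. It does not name admission date or period, and it does not describe an adjusted between-group model.

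**The concern.** Section 5-1.3 presents as largely unanswered the question of whether stimulation improves results when added to traditional therapy. Only the between-group contrast can address that. The before/after change cannot, because every subject also receives about 25 hours of therapy a week (14 individual + 6 group + 5 computer-based, section 5-1.5).

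If all therapy-only records come from before the trial and all tDCS records from during it, a difference in average gain between the two periods adds directly to the estimated tDCS effect. An upward drift can mimic a benefit, and a downward drift can hide one. Recruiting more tDCS subjects does not reduce this bias. It narrows the interval around a shifted value. The plan contains nothing that would show a reader whether such drift had occurred.

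**Working it through.** **1. Reading the sections together.** The 300 are described as already collected (5-1.6), the tDCS subjects as still to be recruited (5-1.5), and all enrolled subjects as receiving active tDCS (tDCS section). If the two periods do not overlap, an indicator for later period equals the indicator for tDCS in every record. A model with intercept, tDCS and period then has three parameters but a design matrix of rank 2. A step change between periods cannot be separated from tDCS. Age, time post-stroke, aphasia type and severity, and lesion measures describe patients. In a between-group model they could adjust for case mix on those variables, but not for change in the program or its testing.

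**2. Inputs for an illustration.** The documents give only the 300. They state no tDCS sample size, significance level, SD, effect size or test, so there is no plan figure to reproduce. Assumed here: n tDCS subjects, a two-sided 5% level, a normal approximation, equal SD of gain in both groups (set to 1), and drift d in SD units.

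**3. Formulas.**
- SE = √(1/n + 1/300)
- False-positive rate with no tDCS effect = Φ(−1.96 + d/SE) + Φ(−1.96 − d/SE)

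For n = 30, SE = √(0.03333 + 0.00333) = 0.1915. For d = 0.2, d/SE = 1.044, so the rate is Φ(−0.916) + Φ(−3.004) ≈ 0.180 + 0.001 = 0.181.

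| Assumed n | SE | d = 0 | d = 0.1 | d = 0.2 | d = 0.3 |
|---|---|---|---|---|---|
| 10 | 0.321 | 5.0% | 6.1% | 9.5% | 15.4% |
| 20 | 0.231 | 5.0% | 7.2% | 13.9% | 25.5% |
| 30 | 0.191 | 5.0% | 8.2% | 18.1% | 34.7% |
| 60 | 0.141 | 5.0% | 10.9% | 29.3% | 56.4% |
| 100 | 0.115 | 5.0% | 13.9% | 41.0% | 73.8% |

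The rate rises with n because d is fixed while the SE shrinks. More historical records do not help: at n = 20 and d = 0.3 the rate is 25.5% with 300 controls and 26.9% with unlimited controls.

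**4. The other direction.** The expected difference is the true effect plus the drift. With n = 30 and an assumed true effect of 0.5 SD, the chance of a significant result is 74.3% without drift. A downward drift of 0.2 SD leaves an expected difference of 0.5 − 0.2 = 0.3 SD, and the chance falls to 34.7%.

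**5. What a concurrent comparison could offer.** With 30 tDCS subjects and 10 to 30 concurrent therapy-only clients (assumed), the SE is √(1/30 + 1/10) = 0.365 down to √(1/30 + 1/30) = 0.258. Against 0.1915 these are about 91% and 35% larger. Such a contrast can support the main one but is too imprecise to decide the result.

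**The case against.** Four points can fairly be made for the plan.

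- **Timing and source are inferred.** A reader might conclude that every one of the 300 is known to come from earlier intakes of this program. The documents do not establish that. They give no dates and do not say outright that the 300 came from this program, although the reference to the same type of therapy suggests it. This point stands, and it is why the confounding is described as apparent. If the 300 came from elsewhere, a site difference would be added to any time difference.
- **No drift is shown.** Changes in staff, software, test versions or referral are possibilities that the documents never mention. The false-positive rates illustrate a formula and do not estimate what will happen in this trial.
- **The aim is exploratory.** Section 5-1.2 asks whether and how tDCS helps and in whom, and the quotation marks around control group suggest that the authors see its limits. That lowers the stakes, but no safeguard follows from it.
- **Concurrent clients are not clean controls.** The Participants section says "Clients who are participating in the University of Michigan Aphasia Program and meet study criteria will be invited to join this study". Eligible clients treated without tDCS will therefore be mainly those who declined or were not approached, and their gains may differ for that reason. This stands and limits how their scores can be used.

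A reader might also infer that the planned standard errors are too narrow because clients treated in the same four-week intake are correlated. The plan describes no between-group model, so there is no stated standard error to fault. This is a separate, optional refinement.

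**Conclusion.** The concern holds for the between-group contrast in 5-1.6. As written, that contrast appears to confound group with period, and neither the subject parameters nor the before/after comparison repairs it. Under the stated assumptions (n = 30, two-sided 5% test), an upward drift of 0.1, 0.2 or 0.3 SD gives a false-positive rate of about 8%, 18% or 35%. The size depends entirely on the assumed n and drift.

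It would go too far to read this as showing that the program changed, or that any change would necessarily favour tDCS. The documents support neither, and drift could equally conceal an effect. The supported conclusion is that the plan offers no way to tell a tDCS effect from drift, although inexpensive checks may be available.

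**What to change.** Amend section 5-1.6 as follows.

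1. Record admission dates for the 300, examine the time trend in their gains, and pre-specify a sensitivity contrast against the most recent part of the 300.
2. Where the same admission and discharge scores already exist, extract them for clients who meet the study criteria but are treated without tDCS during enrolment. Report that contrast as a supportive sensitivity analysis, and state that these clients may be decliners and so self-selected.
3. Include admission date in the between-group model. Without concurrent clients, this term extrapolates the trend within each group and cannot detect a step change. Use only tests given in the same version to both groups, count each person once, and keep anyone who received tDCS out of the therapy-only group.
4. Report all contrasts descriptively, with no rule that they must agree. State that an effect not consistent across them cannot be attributed to tDCS rather than drift.

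Intake-clustered standard errors may be added as an optional refinement.

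The cost is protocol wording, some chart extraction, approval to use the scores, and wider intervals. The concurrent contrast will be imprecise and possibly selected. Item 2 depends on scores that the documents do not confirm are collected routinely, so it applies only where they exist. No additional patients or procedures are needed.
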